9. STATISTICAL METHODOLOGY

9.1 General

Data listings will be provided for all data that is databased. Summary statistics and statistical analysis will only be presented for data where detailed in this SAP. For continuous data, summary statistics will include the arithmetic mean, arithmetic standard deviation (SD), median, min, max and N; for log-normal data (e.g. the PK parameters: AUCs and C_{max}) the geometric mean and geometric CV% will also be presented. For categorical data, frequency count and percentages will be presented. Data listings will be provided for all subjects up to the point of withdrawal, with any subjects excluded from the relevant population highlighted. Summary statistics and statistical analyses will generally only be performed for subjects included in the relevant analysis population. For the calculation of summary statistics and statistical analysis, unrounded data will be used.

Mean change from baseline is the mean of all individual subjects' change from baseline values. Each individual change from baseline will be calculated by subtracting the individual subject's baseline value from the value at the timepoint. The individual subject's change from baseline values will be used to calculate the mean change from baseline using a SAS procedure such as Proc Univariate.

Data analysis will be performed using SAS[®] Version 9.4 or greater.

9.2 Demographics and Subject Disposition

Subject disposition will be listed. The demographic variables age, sex, race, ethnicity, country of enrolment, site ID, body weight, height and body mass index will be summarized and listed. Changes from baseline in weight will also be listed, where baseline is defined as Day -1.

9.3 Pharmacokinetic Assessment

9.3.1 Pharmacokinetic Analysis

The PK parameter estimates will be determined using non-compartmental procedures in validated software program (Phoenix WinNonlin Version 6.4 or later).

Plasma concentrations of LY3298176 will be used to determine the following PK parameters, when possible:

Parameter	Units	Definition
AUC(0-∞)	ng.h/mL	area under the concentration versus time curve from time zero to infinity
$AUC(0-t_{last})$	ng.h/mL	area under the concentration versus time curve from time zero to time t, where t is the last time point with a measurable concentration
$AUC(t_{last}-\infty)$	%	percentage of AUC($0-\infty$) extrapolated
C _{max}	ng/mL	maximum observed drug concentration
t _{max}	h	time of maximum observed drug concentration
t1/2	h	half-life associated with the terminal rate constant (λ_z) in non-compartmental analysis
CL/F	L/h	apparent total body clearance of drug calculated after extra-vascular administration
CL	L/h	total body clearance of drug calculated after intravenous administration
V _Z /F	L	apparent volume of distribution during the terminal phase after extra-vascular administration
Vz	L	volume of distribution during the terminal phase after intravenous administration
V _{SS} /F	L	apparent volume of distribution at steady state following extra-vascular administration
V _{SS}	L	volume of distribution at steady state following intravenous administration
F	NA	absolute bioavailability (based upon geometric mean)

Parts A & B – LY3298176 PK Parameters

Parameter	Units	Definition
AUC(0-τ)	ng.h/mL	area under the concentration versus time curve during one dosing interval (e.g., 168 hours)
AUC(0-72)	ng.h/mL	area under the concentration versus time curve from time zero to 72 hours postdose
C _{max}	ng/mL	maximum observed drug concentration
t _{max}	h	time of maximum observed drug concentration
t1/2	h	half-life associated with the terminal rate constant (λ_z) in non-compartmental analysis

Part C – LY3298176 PK Parameters

Additional PK parameters may be calculated, as appropriate. The software and version used for the final analyses will be specified in the clinical study report. Any exceptions or special handling of data will be clearly documented within the final study report.

Formatting of tables, figures and abbreviations will follow the Eli Lilly Global PK/PD/TS Tool: NON-COMPARTMENTAL PHARMACOKINETIC STYLE GUIDE. The version of the tool effective at the time of PK analysis will be followed.

General PK Parameter Rules

- Actual sampling times will be used in the final analyses of individual PK parameters, except for non-bolus pre-dose sampling times which will be set to zero. For non-bolus, multiple dose profiles, the pre-dose time will be set to zero unless a time deviation falls outside of the protocol blood collection time window which is considered to impact PK parameter derivation.
- C_{max} and t_{max} will be reported from observed values. If C_{max} occurs at more than one time point, t_{max} will be assigned to the first occurrence of C_{max}.
- AUC parameters will be calculated using a combination of the linear and logarithmic trapezoidal methods (linear-log trapezoidal rule). The linear trapezoidal method will be applied up to t_{max} and then the logarithmic trapezoidal method will be used after t_{max} . The minimum requirement for the calculation of AUC will be the inclusion of at least three consecutive plasma concentrations above the lower limit of quantification (LLOQ), with at least one of these concentrations following C_{max} . AUC(0- ∞) values where the percentage of the total area extrapolated is more than 20% will be flagged. Any AUC(0- ∞) value excluded from summary statistics will be noted in the footnote of the summary table.
- Half-life (t_{1/2}) will be calculated, when appropriate, based on the apparent terminal log-linear portion of the concentration-time curve. The start of the terminal elimination phase for each subject will be defined by visual inspection and generally will be the first point at which there is no systematic deviation from the log-linear decline in plasma concentrations. Half-life will only be calculated when a reliable estimate for this

parameter can be obtained comprising of at least 3 data points. If $t_{\frac{1}{2}}$ is estimated over a time window of less than 2 half-lives, the values will be flagged in the data listings. Any $t_{\frac{1}{2}}$ value excluded from summary statistics will be documented in the footnote of the summary table.

- A uniform weighting scheme will be used in the regression analysis of the terminal log-linear portion of the concentration-time curve.
- The parameters based on the last observed quantifiable drug concentration (C_{last}) will be reported.

Individual PK Parameter Rules

- Only quantifiable concentrations will be used to calculate PK parameters with the exception of special handling of certain concentrations reported below the lower limit of quantitation (BQL). Plasma concentrations reported as BQL will be set to a value of zero when all of the following conditions are met:
 - The compound is non-endogenous.
 - The samples are from the initial dose period for a subject or from a subsequent dose period following a suitable wash-out period.
 - The time points occur before the first quantifiable concentration.
- All other BQL concentrations that do not meet the above criteria will be set to missing.
- Also, where two or more consecutive concentrations are BQL towards the end of a profile, the profile will be deemed to have terminated and therefore any further quantifiable concentrations will be set to missing for the calculation of the PK parameters unless it is considered to be a true characteristic of the profile of the drug.

Individual Concentration vs. Time Profiles

- Individual concentrations will be plotted utilizing actual sampling times.
- The terminal point selections will be indicated on a semi-logarithmic plot.

Average Concentration vs. Time Profiles

- The average concentration profiles will be graphed using scheduled (nominal) sampling times.
- The average concentration profiles will be graphed using arithmetic average concentrations.

- The pre-dose average concentration for single-dose data from non-endogenous compounds will be set to zero. Otherwise, only quantifiable concentrations will be used to calculate average concentrations.
- Concentrations at a sampling time exceeding the sampling time window specified in the protocol, or $\pm 10\%$, will be excluded from the average concentration profiles.
- Concentrations excluded from the mean calculation will be documented in the final study report.
- A concentration average will be plotted for a given sampling time only if 2/3 of the individual data at the time point have quantifiable measurements that are within the sampling time window specified in the protocol or ± 10%. An average concentration estimated with less than 2/3 but more than 3 data points may be displayed on the mean concentration plot if determined to be appropriate and will be documented within the final study report.

Treatment of Outliers during Pharmacokinetic Analysis

Application of this procedure to all PK analyses is not a requirement. Rather, this procedure provides justification for exclusion of data when scientifically appropriate. This procedure describes the methodology for identifying an individual value as an outlier for potential exclusion, but does not require that the value be excluded from analysis. The following methodology will not be used to exclude complete profiles from analysis.

Data within an Individual Profile

A value within an individual profile may be excluded from analysis if any of the following criteria are met:

- For PK profiles during multiple dosing, the concentration of the pre-dose sample exceeds all measured concentrations for that individual in the subsequent post-dose samples.
- For PK profiles during single dosing of non-endogenous compounds, the concentration in a pre-dose sample is quantifiable.
- For any questionable datum that does not satisfy the above criteria, the profile will be evaluated and results reported with and without the suspected datum.

Data between Individual Profiles

- 1. If n<6, then the dataset is too small to conduct a reliable range test. Data will be analyzed with and without the atypical value, and both sets of results will be reported.
- 2. If $n \ge 6$, then an objective outlier test will be used to compare the atypical value to other values included in that calculation:
 - a. Transform all values in the calculation to the logarithmic domain.

- b. Find the most extreme value from the arithmetic mean of the log transformed values and exclude that value from the dataset.
- c. Calculate the lower and upper bounds of the range defined by the arithmetic mean ± 3 *SD of the remaining log-transformed values.
- d. If the extreme value is within the range of arithmetic mean ± 3 *SD, then it is not an outlier and will be retained in the dataset.
- e. If the extreme value is outside the range of arithmetic mean ± 3 *SD, then it is an outlier and will be excluded from analysis.

If the remaining dataset contains another atypical datum suspected to be an outlier and $n \ge 6$ following the exclusion, then repeat step 2 above. This evaluation may be repeated as many times as necessary, excluding only one suspected outlier in each iteration, until all data remaining in the dataset fall within the range of arithmetic mean ± 3 *SD of the log-transformed values.

Reporting of Excluded Values

Individual values excluded as outliers will be documented in the final report. Approval of the final report will connote approval of the exclusion.

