7.3. Blinding

Parts A and B are open label. Part C is investigator- and subject-blinded.

In case of an emergency, the investigator has the sole responsibility for determining if unblinding of a subject's treatment assignment is warranted for medical management of the event. The subject's safety must always be the first consideration in making such a determination. If the

investigator decides that unblinding is warranted, it is the responsibility of the investigator to promptly document the decision and rationale and notify Lilly as soon as possible.

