9.3.2 Pharmacokinetic Statistical Methodology

Part A

To assess the relative bioavailability of a single SC dose of LY3298176 administered as a solution formulation (test), compared to a lyophilized formulation (reference), AUC(0- ∞), AUC(0-t_{last}) and C_{max} will be log-transformed and analyzed using a linear mixed effects model with treatment, period, and sequence as fixed effects and subject as a random effect. The difference in least squares means between the test formulation and reference formulation for each parameter will be exponentiated to yield ratios of geometric least squares means and their corresponding 90% CIs.

Example SAS code:

```
proc mixed data=DATA;
    class treatment period sequence subject;
    model log_pk = treatment period sequence / ddfm=kr;
    random subject;
    lsmeans treatment / pdiff cl alpha=0.1;
    ods output lsmeans=lsmeans;
    ods output diffs=diffs;
run;
```

The t_{max} will be analyzed non-parametrically for the same comparison stated above. The Wilcoxon rank-sum test will be used to account for any possible period effect. The median of differences, approximate 90% CI, and p-values will be calculated.

Parts B and C

No formal statistical analysis will be performed. The PK parameters will be summarised by treatment, and listed.

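### For six or more values, the SAP's 3-SD outlier test would flag valid PK data in 18–31% of clean sets if always run, and no all-data result is required after an exclusion

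*SAP*

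**What the plan says.** The rule is in SAP 9.3.1, under *Treatment of Outliers during Pharmacokinetic Analysis*. The preamble makes the procedure optional: it identifies a value that might be excluded, "but does not require that the value be excluded from analysis".

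For data between individual profiles there are two branches.

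- **Fewer than six values:** "Data will be analyzed with and without the atypical value, and both sets of results will be reported".
- **Six or more values:** "an objective outlier test will be used to compare the atypical value to other values included in that calculation". Values are log-transformed, the most extreme is removed, and mean ± 3 SD is computed from the rest. If the removed value is outside, "then it is an outlier and will be excluded from analysis". The test may be repeated, one value at a time, while at least six remain.

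For other questionable values within one subject's profile, "the profile will be evaluated and results reported with and without the suspected datum".

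Excluded values must be documented, and "Approval of the final report will connote approval of the exclusion". SAP 9.3.2 then states that the Part A parameters "will be log-transformed and analyzed using a linear mixed effects model with treatment, period, and sequence as fixed effects and subject as a random effect". Protocol 7.3 says "Parts A and B are open label".

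**The concern.** The test has two weaknesses.

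**Calibration.** Three SD suggests a rare event. Here the largest deviation of n values is chosen first and then judged against an SD from which it has been left out. In small samples that happens often by chance.

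**Reporting and control.**

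1. The preamble does not require exclusion; step e does.
2. The set tested is undefined. For Part A it could be one formulation or both together, since one model covers both.
3. Reporting both ways is required below n=6 and for other questionable within-profile values, but not for n≥6. Planned completers are 16 in Part A, 6 in Part B and 12 in Part C (9 active at 3:1), so every part falls in the branch without it.
4. An exclusion is approved by approving the final report, when results are known, and Part A is open label.

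At stake is Part A's primary result, the solution/lyophilized ratio and its 90% CI, which could rest on data with a valid value removed and no all-data ratio beside it. In Parts B and C, which are descriptive, the effect would be an understated geometric CV.

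**Working it through.** **Inputs from the SAP.** Cut-off 3 SD of the remaining n−1 log values, for every n (9.3.1). Part A: 16 completers, within-subject CV 30% (section 7, 7.1). Part B: 6 completers. Part C: 12 to 16 subjects at 3:1, so 9 to 12 active (section 7).

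**Assumed.** Clean log-normal data; rule run on every set and always followed; between-subject log SD 0.15, 0.30 or 0.60; true ratio 1 unless stated.

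**Step 1: the SAP's precision figure.** The documents give no error rate for the outlier test, so the available check is SAP 7.1.

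- σ_w = √ln(1 + 0.30²) = 0.2936.
- Expected 90% CI half-width at n=16: t(0.95, 14) × σ_w × √(2/16) = 1.761 × 0.2936 × 0.3536 = 0.183.
- With 90% assurance: 0.183 × √(χ²(0.90, 14)/14) = 0.183 × √(21.06/14) = 0.224.
- Taking σ_w as 0.30 gives 0.229.

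The SAP's 0.227 lies between these, so the Part A set-up is reproduced.

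**Step 2: flag rate per clean set.** For one given value, the deviation from the mean of the other n−1 values, divided by their SD and by √(1 + 1/(n−1)), follows t with n−2 df. Summing over n values:

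P(flag) ≈ n × P(|t(n−2)| > 3/√(1 + 1/(n−1)))

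| n | t limit | two-sided P | n × P | Simulated (200,000 sets) |
|---|---|---|---|---|
| 6 | 2.739 | 0.0520 | 31.2% | 31.3% |
| 9 | 2.828 | 0.0255 | 22.9% | 22.9% |
| 12 | 2.872 | 0.0166 | 19.9% | 19.9% |
| 16 | 2.905 | 0.0115 | 18.5% | 18.4% |
| 20 | 2.924 | 0.0091 | 18.1% | 18.0% |

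With repetition, about 3.4% of sets at n=16 lose a second value. At n=6 a second removal is impossible, because five values remain.

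**Step 3: Part A trials losing a value, per parameter.** If the two formulations were independent, the rate would be 1 − (1 − 0.1845)² = 33.5%. Simulated 2×2 crossovers (8 per sequence, 12,000–15,000 per setting) give 30–34% when each formulation is tested and 14–19% when all 32 values are tested together.

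**Step 4: effect on the ratio and CI.** Each trial was refitted by REML with the SAP's model terms. Satterthwaite df were used where the SAP specifies Kenward-Roger.

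| Each formulation tested | Mixed model | Complete pairs |
|---|---|---|
| 90% CI coverage, all trials | 86–89% | 87–89% |
| Coverage, trials losing a value | 80–88% | 83–88% |
| Mean shift in ratio when a value is lost | 5–6% | 3–5% |

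In the trials that lose a value, keeping all data gives 89–91% coverage. The 95th percentile of the mixed-model shift is 10–12%, against an expected half-width of about 0.18 on the log scale. Mean CI width changes by −3% to +1%. When all 32 values are tested together, coverage stays about 90%.

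**Step 5: selective use.** With a true ratio of 1.15, and flagged values dropped only when that moves the ratio toward 1, 14–15% of trials are altered. The ratio in those trials falls by 4–5%, and coverage stays about 90%.

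**Step 6: descriptive parts.** A set of six that loses a value keeps on average 53% of its log SD.

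**The case against.** The strongest reply is that 18–31% is not the rate of the rule as written. The SAP applies the test to a value already thought atypical and leaves exclusion to judgement, so the actual rate is unknown and probably lower. The SAP also sets no target error rate, so calling the test miscalibrated is a judgement against customary levels such as 5%. Both points stand: the percentages are upper bounds. Discretion does not supply the missing all-data result, however, and it leaves open when the decision is taken.

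Second, the rule follows the average-concentration rules in 9.3.1, and 9.3.2 does not mention outliers. It might therefore concern only concentrations or summary statistics, in which case the Part A coverage and shift figures would not apply. That reading cannot be ruled out, but it fits poorly with a preamble that refers to PK analyses in general. The ambiguity is itself a reason to define the set tested.

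Third, the harm is limited. A removal rule symmetric on the log scale introduces no systematic bias in the ratio, the coverage loss nearly disappears at the largest between-subject SD, and no margin is visible. This stands and limits the severity.

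Fourth, safeguards exist. Exclusions are documented, databased data are listed, complete profiles cannot be removed, and repeats stop once the remaining values are in range. A reader with the listings could rebuild the all-data ratio, but the report need not show it.

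The preamble and step e can be reconciled by reading step e as the outcome once the test is used. That wording conflict is the weakest of the four gaps.

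**Conclusion.** The concern holds and should be fixed. Two parts are firm. The SAP requires both-ways reporting below n=6 but not at n≥6, the branch that covers every planned part. And a fixed 3-SD limit on a pre-selected extreme flags a valid value in 18–31% of clean log-normal sets for n from 6 to 20.

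The consequence for Part A is modest and depends on reading the rule as applying to PK parameters and on its being run and followed every time. Tested per formulation, coverage is 86–89% against a nominal 90%, with a typical 5–6% move in the ratio when a value is lost. Tested on all 32 values together, coverage is essentially unaffected. These figures also rest on the SAP's 30% within-subject CV and the assumed between-subject SDs. The rate under discretionary use cannot be computed. With no equivalence margin in the visible text, no pass/fail decision changes; what is lost is assurance that the reported ratio uses all valid data.

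**What to change.** Amend SAP 9.3.1 as follows.

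1. State that the Part A mixed model and the Part B and C summaries keep all valid PK parameter values.
2. Replace step e: a value outside the range is flagged and triggers a sensitivity analysis without it, with both results reported at every n. This extends the SAP's own n<6 rule. Adjust the repetition paragraph, which now assumes an exclusion.
3. Define the set tested, for example one parameter within one formulation.
4. Reserve exclusion for documented dosing or assay errors, recorded before the formulation comparison is run.

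If a numerical screen is wanted, the limit can depend on n. This is optional once items 1 and 2 are in place. For a 5% flag rate per clean set, the limits are about 5.3 SD at n=6, 4.2 at n=9, 3.8–3.9 at n=12 and 3.7 at n=16. For 5% per Part A parameter, they are about 4.0 SD if each formulation is tested and 3.4–3.5 SD if all 32 values are tested together.

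The cost is SAP wording and at most one sensitivity table per affected parameter. The downside is that a truly aberrant value stays in the main analysis and may widen the CI; the sensitivity result would show this.

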9.3.2 Pharmacokinetic Statistical Methodology

Part A

To assess the relative bioavailability of a single SC dose of LY3298176 administered as a solution formulation (test), compared to a lyophilized formulation (reference), AUC(0- ∞), AUC(0-t_{last}) and C_{max} will be log-transformed and analyzed using a linear mixed effects model with treatment, period, and sequence as fixed effects and subject as a random effect. The difference in least squares means between the test formulation and reference formulation for each parameter will be exponentiated to yield ratios of geometric least squares means and their corresponding 90% CIs.

Example SAS code:

```
proc mixed data=DATA;
    class treatment period sequence subject;
    model log_pk = treatment period sequence / ddfm=kr;
    random subject;
    lsmeans treatment / pdiff cl alpha=0.1;
    ods output lsmeans=lsmeans;
    ods output diffs=diffs;
run;
```

The t_{max} will be analyzed non-parametrically for the same comparison stated above. The Wilcoxon rank-sum test will be used to account for any possible period effect. The median of differences, approximate 90% CI, and p-values will be calculated.

Parts B and C

No formal statistical analysis will be performed. The PK parameters will be summarised by treatment, and listed.

